8.2.3 Statistical Software and General Requirements

Data are analyzed by the internationally recognized statistical software (such as SAS 9.2 software (SAS Institute Inc., Cary, NC, USA)), and pharmacokinetic parameters are calculated by WinNonlin software or other recognized softwares.

A complete, detailed statistical analysis is described in the statistical analysis plan, and the statistical analysis plan is finalized prior to locking the database.

8.2.4 Interim Analyses

A interim analysis is performed when at least 30 subjects complete 4 cycles and 40 subjects complete 2 cycles of evaluation in the randomized comparison part of this study as to compare the safety and tolerability of two different administration methods of Fruquintinib. The primary parameters are statistically analyzed and combined with efficacy parameters

for comprehensive evaluation to determine the recommended dose group in phase II/III study for expansion part.

8.3 Sample size

About 60 subjects are planned to be enrolled.

Here, 40 subjects are enrolled into the randomized comparison part, and approximately 20 more subjects are enrolled into the single-arm expansion part.

Randomized comparison part:

Group A (4 mg, qd, daily) consists of 20 patients;

Group B (5 mg, qd, 3-week on/1-week off) consists of 20 patients;

Expansion part:

Group B (5 mg, qd, 3-week on/1-week off) consists of approximately 20 patients.

9 Data Quality Assurance

Electronic data management system (DASforeCDM5.0) is used for this trial.

Establishment of electronic case report form (eCRF): eCRF is constructed by data administrator according to study protocol and medical record.

Allocation of authorities: the data administrators create the account respectively according to different identities, including investigator, sponsor, monitor and auditor, and are authorized different permissions to access eCDM. For example, investigators at each site can only find the content at their site and have the right to modify the data, the sponsor is limited only to look through all the cases; monitor and auditor can read the cases at each site, insert remarks or questions but have no right to modify the data.

Data entry: clinical investigators or their designated data entry clerk (clinical coordinator) enter the data from the medical records in the eCRF promptly and accurately. eCRF is not used as the original record, its content originates from medical records.

[figure not shown]
Questions on the data and answers: monitors monitor the data through eCDM and raise questions on line at any time when they find questions, the investigators answer the questions on line and modify wrong data, monitors could repeat their questions when necessary.

Data lock and export: the data are locked by the data administrator after each subject complete the trial and all the data are confirmed correct by the monitor, until the lock of the data from the last subject. The data are exported into the designated database by the data administrator after complete data lock, and submitted to statisticians for analysis.

eCRF is printed for archive at the end of study, if required. Data management center will maintain the electronic data until 5 years after its launch in the market. The data management center can open the system at any time after appointment during this period if

SFDA needs to check.

EDC System Emergency Plan

10 Study committee

This study will establish a Data Monitoring Committee (DMC). The Committee consists of and is charged by the medical monitor of the sponsor, safety data monitor, and the principal investigator.

DMC will review safety data. Safety data include: Demographic data, adverse events, severe adverse events, and laboratory abnormal values.

After data review, DMC will provide suggestions whether the study will be continued, and whether it is required to revise the protocol or to discontinue the study. These will be determined eventually by Hutchison Medi Pharma (Shanghai) Co., Ltd.

11 Ethics

11.1 Local Regulations/Declaration of Helsinki

The Investigator will guarantee that the study will be conducted in strict accordance with the principle of the "Declaration of Helsinki" and/or with the laws and regulations of the country where the study is conducted, and provide maximized protection for patients. The study must adhere to the principles in the ICH Guideline for "Good Clinical Practices" (since Jan 1997) or local laws, to provide maximized protection for patients.

11.2 Informed Consent

The responsibilities of the Investigator or the Investigator Designee (if allowed by local laws) are to explain adequately the purpose, method, expected benefits, and potential hazards of the study, and obtain the informed consent from each subject participating in the study. For a patient who is not qualified to or cannot provide a legal informed consent, a written informed consent must be obtained from his/her legal guardian. If a patient and his/her legal guardian cannot read, then the whole discussion course of informed consent must

be witnessed by a notary. After the patient and his/her guardian agree verbally to participate in the study, then the notary signs in the informed consent form, to prove that the information of the informed consent is explained and understood accurately. The Investigator or his/her designee must also explain that, the patient is free to refuse to participate or discontinue the study in any reason at any time. The content of case report form (including some part that are used to record patient's informed consent) of this study must be filled correctly. If a new safety information result in any obvious change of the risk/benefit evaluation, then the informed consent must be reviewed and updated if necessary. All patients (including those being treated) shall be informed of such new information, and provided with a revised informed consent, and continue the study if they give the corresponding informed consent.

11.3 Independent Ethics Committee/Institutional Review Board

The protocol and any relevant materials provided to patients (such as patient's manual or study description), as well as advertisement and compensation given to patients will be submitted to Independent Ethics Committee by the Investigator. Prior to start of the study, it must be approved by the Ethics Committee, and is recorded in the form of Letter to the Investigator, including the dates for conference of the Ethics Committee, and for granting approval.

After receiving the approval document from the Ethics Committee, if any change is made to the protocol, investigator shall also submit it to the Ethics Committee accordance with the procedure and the regulatory requirements.

12 Conditions to Change the Protocol

The protocol and the study flow cannot be changed, without mutual agreement by the Principal Investigator and Hutchison Medi Pharma (Shanghai) Co., Ltd.

If the protocol must be revised, the revised content or the new version of the protocol (revision) must be submitted to the Ethics Committee for review to obtain a written approval. If required, it is also submitted to a local regulatory authority or is approved, and must follow the requirements of the local regulatory authority.

If the revision of the protocol requires to change the informed consent in study site, then Hutchison Medi Pharma (Shanghai) Co., Ltd. and the Ethics Committee of the study site must be notified. A written approval must be obtained from Hutchison Medi Pharma (Shanghai) Co., Ltd. and the Ethics Committee for application of the revised informed consent.

Hutchison Medi Pharma (Shanghai) Co., Ltd. will distribute the protocol revision and the new version to each principal investigator, and then the Principal Investigator will distribute such documents to the corresponding Ethics Committee and other study personnel.

13 Condition to End the Protocol

The sponsor and the Investigator have the right to terminate the study at any time. If it is necessary to terminate the trial, it must be ended through mutual inspection and negotiation. To discontinue the study, Hutchison Medi Pharma (Shanghai) Co., Ltd. and the Investigator will ensure to maximize patients' benefits.

14 Record, Storage, and Access to the Study Documents

14.1 Storage of Investigator's Documents/Records

The Investigator shall agree to keep all research data, including confirmation of all participating subjects (which may check efficiently different recorded data, such as eCRF/CRF and hospital original records), original informed consent forms of all patients, eCRF/CRF, and detailed records for drug dispensation, etc.

All data of the clinical trial are property of Hutchison Medi Pharma (Shanghai) Co., Ltd., and shall not be disclosed to any person unrelated with this trial in any form, without agreement by the sponsor. The related data of the study can only be published after agreement by the sponsor.

14.2 Original Documents and Background Information

The original documents may prove existence of patients, as well as integrity of collected data. The original data are archived in the study site of the Investigator.

The data in eCRF/CRF transferred from the original documents must be consistent with the original documents, and any difference must be explained. According to the trial, the Investigator may require previous medical records of transferral records, or may require current medical records.

All data in eCRF/CRF must be originated from original documents.

14.3 Direct Access to Original Data and Documents

The Investigator/Institution will agree to carry out trial-related examination, audits, IRB/IEC review, as well as examination by the regulatory authority, and provide direct access to all relevant original data/documents. eCRF/CRF as well as all source documents, including pathology records, as well as copies of laboratory tests and medical examinations, must be available for examination by the clinical monitor, auditor, and health regulatory authority at any time. Clinical Research Associate (CRA) as well as the auditor may review all eCRF/CRFs as well as written informed consents.

15 Study monitoring

Prior to enrollment of the first subject, the authorized monitor on behalf of Hutchison Medi Pharma (Shanghai) Co., Ltd. shall be at the study site:

- ◆ Ensure the facilities and equipment available;

- ◆ Discuss with the Investigator (or other study personnel) the responsibilities of the research members and monitors in the study, and sign relevant agreements;
- ◆ During the study, the monitor shall visit the study site regularly, and keep in close contact with the Investigator;
- ◆ Provide sufficient information and support to the investigators;
- ◆ Ensure that the research facilities and equipment in place;
- ◆ Ensure that the group follows the protocol, and the data are recorded accurately in eCRF/CRFs, and study drugs are counted;
- ◆ Ensure to complete verification of the data (verify that the data in eCRF/CRFs are consistent with the hospital's medical records, and other records related with the study).It is required that the original records of each subject may be obtained.

If the Investigator requires more information and suggestions, the monitor and other representatives of Hutchison Medi Pharma (Shanghai) Co., Ltd. will visit the study site.

16 Confidentiality of the Trial Documents and Patients' Records

The Investigator must ensure to maintain patients' anonymity and prevent to disclose a patients' identity to any unauthorized party. Patients cannot be identified with a patient's name but only with his/her identification code in CRF/ECRFs or other documents submitted to the sponsor. The Investigator shall record an enrollment registry form of patients, to display a patient' code, name, and address. The Investigator shall store strictly certain documents such as a patient's informed consent, and never submit to Hutchison Medi Pharma (Shanghai) Co., Ltd.

Appendix 1 ECOG performance status

The patients are graded according to ECOG performance status, and the criteria are described as follows:

grades	ECOG
0	Fully active, able to carry on all pre-disease performance without restriction
1	Restricted in physically strenuous activity but ambulatory and able to carry out work of a light or sedentary nature, e.g., light house work, office work
2	Ambulatory and capable of all selfcare but unable to carry out any work activities. Up and about more than 50% of waking hours
3	Capable of only limited selfcare, confined to bed or chair more than 50% of waking hours
4	Completely disabled. Cannot carry on any selfcare. Totally confined to bed or chair
5	Death

Appendix 2 RECIST version 1.1 for Tumor Evaluation

RECIST version 1.1

(Response Evaluation Criteria in Solid Tumors RECIST Version 1.1)

As RECIST version 1.1 is not published in any formal Chinese version, and this version is an internal translation. Please refer to the English version for more detailed information.

1 Background

1.1 History of the RECIST Criteria

To evaluate any change of tumor burden is an important feature in clinical evaluation of cancer treatment. The times to tumor reduction (objective response) and progression of disease are important judgment endpoints in a clinical trial of cancer. To screen new antitumor drugs, the evidences from studies of many years supports that tumor reduction is used as an endpoint for Phase II trial. Those studies suggest that, for solid tumors, a drug that may promote tumor reduction in some patients may be later proved possibly (imperfect though) to increase a patient's overall survival or allow him/her to have an opportunity to enter event evaluation in a Phase III randomized trial. Presently, among the variables to evaluation treatment effects in Phase II screening trials, objective response is more reliable than any other biomarkers. Moreover, among Phases II and III clinical trials for drug development, the time to progression of disease (or progression-free survival) is gradually used as an endpoint to judge effectiveness in clinical trials in severe disease, and is based on anatomic measurement of tumor size.

However, the two judgment endpoints i.e. objective response and time to progression of disease are valuable only when the widely accepted and easy-to-use criteria and rules are established on the basis of tumor burden anatomy. In 1981, the World Health Organization (WHO) first published the criteria for response in tumors, which have been mainly used in trials in which tumor response is a primary endpoint. The WHO criteria introduced the overall evaluation concept of tumor burden by measuring and totaling the 2-dimensional of tumor, and judged treatment response by evaluating a change during treatment since baseline. However, in a dozen years after publication of the criteria, the Cooperative Group using the criteria and pharmaceutical companies modified them to adapt new technologies or proposed unclear points in the original literatures, leading to confusion in interpreting the results of a trial. In fact, the application of various response criteria resulted in distinct differences of treatment effects by the same therapeutic method. For those questions, an international work group was established in the mid-19th century to standardize and simplify the criteria for response. The new criteria, also known as RECIST (Response Evaluation Criteria in Solid tumors) was published in 2000. The initial key features of RECIST included: Determination of minimum measurable lesions; description of lesions to be followed (10 lesions at maximum; 5 lesions per organ at maximum); use of 1 dimension other than 2 dimensions; and overall evaluation of tumor burden. Later, those criteria have been used widely by academic communities, cooperative groups, and the pharmaceutical

industry. The initial endpoints of the criteria are objective response or progression of disease. Moreover, the competent authority accepts RECIST as suitable criteria for those evaluation.

2. Purpose of the Guideline

The Guideline describes a standard method for measuring solid tumors, and clarifies the objective judgment criteria for change of tumor size, used in clinical trials in adults and pediatric patients. It is expected that those criteria will be used in trials in which objective response is used as the primary study endpoint, as well as in trials using steady-state disease evaluation or tumor progression or analyzing time to progression as variables, as the measurement of all therapeutic effects are based on evaluation of anatomical tumor burden and its change. In this article, the proportion of patients meeting the inclusion criteria are not hypothesized. The patients adopt one trial endpoint that may predict effectiveness of one drug or therapeutic regimen whose definition is dependent on type of tumor in the ongoing trial and special drugs under investigation. The trial protocol must include an appropriate statistics section, where the sample size of the trial and the effectiveness parameters on which the inclusion criteria are based are defined. This Guideline provides the definition and criteria to judge tumor response, and also proposes suggestions for reporting criteria of the results of a clinical trial using tumor response as the trial endpoint.

Although those guidelines may be used in research of malignant cerebral tumors, the criteria for evaluation of response have been published separately in this field. As the international rules for evaluation of lymphoma response have also been published separately, this Guideline is not used in research of malignant lymphoma.

Finally, many oncologists follow patients' malignant disease by multiple imaging investigations in their daily clinical practices, and determine further treatment regimen on the basis of both objective and symptom criteria. Those RECIST guidelines may play an important role only when the treatment oncologist judge them as rational.

3. Baseline Tumor Measurement

3.1 Definition

At baseline status, tumor lesion/lymph nodes are divided into measurable and immeasurable categories as follows:

3.1.1 Measurable

Neoplastic lesion: It must measure accurately to at least one size of not less than the lower limit (of instrument detection) (the maximum diameter in the measuring instrument will be recorded):

- A 10-mm size is scanned by CT (in a thickness of not less than 5 mm; see Appendix III, Guideline for Imaging).

- For clinical test, 10 mm is measured by a caliper (a lesion that cannot be measured by a caliper is recorded as immeasurable).
- 20 mm is examined by chest X-ray radiography.

Malignant lymph nodes: When evaluated by CT scanning (CT scanning layer thickness is not more than 5 mm as suggested), it is considered as pathological expansion and measurable lesion only when the short axis of lymph nodes must be up to 15 mm. The short axis length is measured and followed in preoperative and subsequent practices. The data for measurement of lymph nodes may be obtained from notes under "Preoperative Documents for Target and Non-target Lesions".

3.1.2 Immeasurable (Tumor)

All the other lesions, including small lesions (the maximum diameter is less than 10 mm, or the short axis of pathological lymph nodes ranges between 10- < 15 mm), as well as truly immeasurable lesions. The lesions considered as truly immeasurable lesions include: Pharmacologically confirmed meningeal diseases, ascites, pleural effusion or pericardial effusion, inflammatory breast diseases, lymph vessel-involved skin or pulmonary, abdominal masses/abdominal organ gigantisms, which cannot be measured by imaging reconstruction technique.

3.1.3 Special Considerations for Measurable Lesions

Special attention has to be paid to bone lesions, cystic lesions, or lesions previously treated locally:

Bone lesions:

- Bone scanning, PET scanning, or plain radiography are considered inadequate for measuring bone lesions. However, those techniques may be used to confirm pharmacologically presence or absence of bone lesions.
- If the soft tissue part meets the definition of the above measurable lesions, lytic bone lesion with discernible soft tissues, or mixed acute lytic bone lesion may be evaluated by cross imaging techniques such as CT or MRI, then they are considered as measurable lesions.
- Osteogenic lesions are immeasurable.

Cystic lesions:

- Simple cysts meeting the X-ray definition of the inclusion criteria should not be considered as malignant lesions (they are not measurable and are not immeasurable), as they are simple cysts by the definition.
- Meeting the above definition of measurable lesion, "cystic lesions" characterized by cystic metastasis may be considered as measurable lesions. However, in case of

noncystic lesions present in the body of the same patient, the target lesions are included preferentially.

Lesions previously treated locally:

- The lesions located in the previous irradiation area or at the site receiving other local treatment are usually considered as measurable, unless it has proved that the lesions still continue. The protocol should explain under what conditions those lesions are considered measurable.

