PK study	
To explore the pharmacokinetic (PK) profile of two different administration methods of Fruquintinib (4mg qd daily vs. 5mg qd 3-week on/1-week off), and to explore the relationship between PK and preliminary pharmacodynamic parameters as well as the main safety parameters

Inclusion Criteria	
All the following conditions must be met:
 
 Fully understanding of this study and voluntary signature of the informed consent form; Histologically and/or cytologically confirmed advanced colorectal cancer after

-
- 2nd-line or above treatment failure;
3. No systemic antitumor treatment or radiotherapy, immunotherapy, biological or hormone therapy in the past 4 weeks; no treatment with VEGFR inhibitor;
 4. Age = 18-70 years
 5. Body weight >40KG;
 6. Eastern cooperative oncology group (ECOG) score 0 or 1, and no exacerbation within 7 days;
 7. Evaluation of cardiac function: left ventricular ejection fraction $\geq 50\%$ (echocardiography);
 8. Definitely measurable lesion according to RECIST1.1;
 9. Expected survival > 12 weeks.
-

Patients meeting any of the following conditions must be excluded from this study:

1. Absolute neutrophil count (ANC) $< 1.5 \times 10^9/L$, platelet count $< 80 \times 10^9/L$ or hemoglobin $< 9g/dL$ in the laboratory test performed within one week prior to enrollment;
 2. Serum total bilirubin, glutamic-pyruvic transaminase, glutamic-oxaloacetic transaminase and alkaline phosphatase exceeding normal range (based on the normal value at clinical study site); alkaline phosphatase more than $2.5 \times ULN$ for patients with liver metastasis;
 3. Serum creatinine exceeding the upper limit of normal range (based on the normal value at clinical study site) or creatinine clearance lower than 50ml/min;
 4. Systolic blood pressure $\geq 150mmHg$ and/or diastolic blood pressure $\geq 100mmHg$ regardless of the use of antihypertensive agent;
 5. Serum potassium exceeding normal range with clinical significance, regardless of the supplementation of potassium preparation;
 6. Serum calcium or magnesium exceeding normal range with clinical significance, regardless of any supplementation;
 7. Urine protein 2+ or above, or 24-hour amount of urine protein $\geq 1.0g/24h$;
 8. Evidence of intestinal cavity infiltration of the tumor (with possibility of potential bleeding);

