In the 15 evaluable patients in 4.0mg dose group, 13 subjects reached SD or above (7 PRs, 6 SDs \geq 8 weeks; patients with partial response had colorectal cancer, gastric cancer, lung cancer and breast cancer) and the objective response rate was up to 46.66%. Although 2 grade 3 hepatic impairment, 2 grade 3 hand-foot syndrome, 1 grade 3 proteinuria, 1 grade 3 asthenia and 1 grade 3 stomatitis that were possibly related with the study drug, and 2 >grade 3 thrombocytopenia that were related with the study drug occurred in this dose group, all the symptoms were resolved or relieved after discontinuation of the drug and active treatment. Therefore, significant antitumor activity and good tolerability were shown in 4.0mg dose group.

In the 7 evaluable patients in 5.0mg 3-week on/1-week off group, 6 subjects reached SD or above, including 4 PRs, the objective response rate was up to 57.14%, and patients with partial response had breast cancer, neuroectodermal malignancy, nasopharyngeal carcinoma and submandibular gland carcinoma. Only 1 grade 3 hand-foot syndrome that was related with the study drug occurred in this dose group, and was resolved after transient discontinuation of the drug and active treatment. Thus a significant antitumor activity and good tolerability were shown in 5.0mg 3-week on/1-week off group as well.

In combination with the preliminary results on safety and efficacy from the tolerability clinical trial and expansion part of Fruquintinib, the recommended doses for phase Ib clinical trial are 4.0mg qd po daily and 5.0mg qd po 3-week on/1-week off.

(3) Preliminary results of the interim analysis of phase Ib trial (as of Sep. 20, 2013):

A total of 40 (1:1) subjects were enrolled in the randomized phase Ib clinical trial comparing two different administration methods of Fruquintinib as 3rd-line or above therapy for advanced colorectal cancer, including 27 males and 13 females; 24 colon carcinoma and 16 rectal cancer.

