4.2 Enrollment criteria

Subjects can be enrolled only when all the following criteria are met in accordance with the guidance on the antitumor drug clinical trial:

1. Fully understanding of this study and voluntary signature of the informed consent form;
2. Histologically and/or cytologically confirmed advanced colorectal cancer after 2nd-line or above treatment failure;

3. No systemic antitumor treatment or radiotherapy, immunotherapy, biological or hormone therapy in the past 4 weeks; no treatment with VEGFR inhibitor;
4. Age = 18-70 years
5. Body weight >40KG;
6. Performance status score (ECOG score) ≤ 1 (0-1) with no exacerbation within 7 days;
7. Evaluation of cardiac function: left ventricular ejection fraction $\geq 50\%$ (echocardiography);
8. Definitely measurable lesion;
9. Expected survival > 12 weeks.

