6.2.1.2 Assessment of effectiveness

The tumor is evaluated in accordance with RECIST1.1 criteria, and the detailed evaluation criteria are provided in Appendix 2. The radiological evaluation of tumors could use CT or MRI as decided by investigators, however, the apparatus and technical parameters should keep consistent throughout the study; contrast agent should be used in case of no contraindications. If the tumor evaluation has been performed 14-21 days before the first dose, and the same method and apparatus are used in the same hospital, this evaluation could be used as the baseline tumor evaluation. The baseline tumor evaluation should include neck, chest, abdomen, pelvis and any other sites that are suspected to have tumor lesions. Bone scan should be used for follow-up of the disease in patients with bone metastasis.

Record of target lesions: number, site and description of lesions, the maximum diameter measured for each lesion (except lymph node) and the minimum diameter measured for lymph node, sum of diameters including all the target lesions;

Subjects will receive the first tumor evaluation after 2 cycles of treatment, and one evaluation every two cycles subsequently, until progression of disease. If complete response or partial response occurs, it needs to be confirmed after 4 weeks. If the patient interrupts the dose for adverse drug reaction or other reasons, the tumor evaluation will be performed once every 8 weeks as originally scheduled. If the patient discontinues the study drug within 56 days, the tumor evaluation should be performed as early as possible after discontinuation of the drug.

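### Appendix 2 reverses the measurability condition for previously irradiated or locally treated lesions, and the protocol body gives no rule of its own

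*Protocol*

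**What the plan says.** The synopsis version of inclusion criterion 8 asks for a "Definitely measurable lesion according to RECIST1.1". The body version (4.2 item 8) says only "Definitely measurable lesion". Section 6.2.1.2 ties assessment to the appendix: "The tumor is evaluated in accordance with RECIST1.1 criteria, and the detailed evaluation criteria are provided in Appendix 2".

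On lesions in a previously irradiated area or treated locally in another way, Appendix 2, 3.1.3 says that those "at the site receiving other local treatment are usually considered as measurable, unless it has proved that the lesions still continue". The sentence after it reads "The protocol should explain under what conditions those lesions are considered measurable".

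Earlier radiotherapy is not a bar to entry. Inclusion criterion 3 asks for "No systemic antitumor treatment or radiotherapy, immunotherapy, biological or hormone therapy in the past 4 weeks", so a lesion irradiated before that window may be present at baseline.

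The opening of Appendix 2 describes the text as an internal translation and adds: "Please refer to the English version for more detailed information".

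**The concern.** The exception is attached to the wrong case. Proof that a treated lesion is still there should support using it to follow the disease, yet here that proof takes away its measurable status. A treated lesion about which nothing has been shown keeps that status.

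Two decisions at baseline depend on this rule: whether the patient meets criterion 8, and which lesions enter the sum of diameters. If a site applies the text as written, tissue already controlled by earlier radiotherapy or other local therapy can be a target lesion, and its stability may be credited to fruquintinib. The expansion part is the most exposed. Its primary efficacy endpoint is progression-free survival at Week 16, and it has no concurrent comparator.

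**Working it through.** No sample-size or error-rate figure is involved. The check is a reading of the text, with one line of arithmetic for scale.

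1. **The rule taken literally.**
   - Treated lesion not shown to persist: measurable.
   - Treated lesion proved to persist: not measurable.

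   Both outcomes are the reverse of what a measurability rule is for.

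2. **The rule against the next sentence.** That sentence asks the protocol for the conditions under which such lesions are measurable. Such conditions are needed only if these lesions do not count without them. The first sentence starts from the opposite default, so the two cannot both stand.

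3. **Whether the body settles it.** Section 4.2 item 8 adds no condition. Section 6.2.1.2 covers imaging method, sites, timing and recording of target lesions, but not previous local treatment. The target population (4.1) requires progression after earlier lines, but not progression in the lesion chosen as target. The size thresholds in Appendix 2, 3.1.1 and 3.1.2 still apply, but they test size and not activity since treatment. No overriding rule was found.

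4. **Route to the endpoints.**
   - *Stable disease and DCR:* a controlled lesion tends to stay the same size, which favours stable disease of at least 8 weeks (6.2.1.1). Direction: upward.
   - *16-week PFS:* target-lesion progression needs a 20% rise in the sum over its smallest value, and at least 5 mm (Appendix 2, 4.3.1). If controlled lesions make up a share s of that smallest sum and do not change, the remaining target lesions must grow by 0.20/(1 − s). At s = 0 this is 20%; at s = 1/2, taken only as an illustration, it is 0.20/0.50 = 40%; at s = 1 the target-lesion criterion cannot be met. Direction: upward.
   - *ORR:* a partial response needs a 30% fall from the baseline sum. A lesion still shrinking from earlier therapy would help reach it; a fixed residual would hinder it. Direction: uncertain.

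5. **What limits the route.** Target lesions are to represent all involved organs, with at most five in total and two per organ (Appendix 2, 4.2). A treated lesion therefore dominates the sum only when there is little other measurable disease. A new lesion or clear non-target progression is progression whatever the target lesions do (Appendix 2, 4.3.3, 4.3.5 and Table 1). Death is a PFS event (8.1).

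6. **Scale.** The expansion part has about 20 patients (3.2, 8.3). One patient wrongly counted as progression-free at Week 16 moves a simple proportion by 1/20 = 5 percentage points. For k such patients the shift is 5k points. The protocol gives no value for k and nothing from which to derive one.

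**The case against.** The strongest reply is that this is a translation slip with little practical reach. The appendix says it is an internal translation, and the synopsis ties criterion 8 to RECIST 1.1 itself. The same appendix has other plain slips: in 3.1.1 the CT slice thickness is given as not less than 5 mm for tumour lesions but not more than 5 mm for lymph nodes. A careful reader would notice that the bullet contradicts itself. This part of the reply stands, and a reader who inferred that the sponsor chose to count treated lesions by default would go beyond the documents. It does not remove the error. The pointer to the English version is for more detail and does not say that the English text prevails. Nor would that version supply conditions that the appendix asks this protocol to set.

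A reader might also infer a sizeable inflation from the interim description, "24 colon carcinoma and 16 rectal cancer", on the ground that rectal cancer is often irradiated. The documents do not support this. Those are primary sites in the randomized part, not counts of irradiated patients, of patients with only treated target lesions, or of expansion patients.

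Finally, the consequence is bounded. No threshold or test is attached to the 16-week rate (8.2.2, 8.3), and the expansion regimen was chosen from the randomized part, where both groups were assessed under the same text. These points limit the severity but leave the wording wrong.

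**Conclusion.** The point holds as an error in the stated rule, most likely of translation. Appendix 2, 3.1.3 reverses the condition for previously irradiated or locally treated lesions and conflicts with its own next sentence, and the body does not supply the missing condition. Followed literally, it lets a controlled treated lesion satisfy criterion 8 and serve as a target, and bars a treated lesion proved to persist.

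The possible bias is upward for stable disease, DCR and the expansion part's 16-week PFS rate. No direction can be claimed for ORR. The total size cannot be computed. The 5 points per patient apply only to a patient whose target lesions are only or mainly treated sites, who has no new lesion, non-target progression or death by Week 16, and who would have been scored as progressed under a correct rule. Any percentage for the trial as a whole would be a guess. The correction is worth making because the rule governs eligibility and target-lesion choice and is cheap to put right.

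**What to change.** - In Appendix 2, 3.1.3, replace the sentence with one saying that lesions in a previously irradiated area, or treated with other local therapy, are not measurable and may not be target lesions unless progression in that lesion has been documented since the local therapy.
- State the same condition in 4.2 item 8 (and the matching synopsis item) or in 6.2.1.2, so that the protocol gives the explanation its appendix asks for.
- For patients already enrolled, flag those whose only target lesion was previously treated, and report DCR and the 16-week PFS rate with and without them.

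The cost is a sentence in the appendix, a condition in the body, and a sensitivity summary. No new procedure is needed. The downside is small: a few patients with only treated, non-progressing lesions become ineligible.
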